3.1.1.1.4. Onset Day of Each Local Reaction After Each Dose and Any Dose

The onset day of each local reaction will be derived after each dose. Onset day is defined as the first day of reporting any reaction of any severity.

The onset day for each local reaction after any dose will be derived after any VLA15 dose for the VLA15 group, and after any placebo dose for the placebo group, based on the variable of the first (earliest) onset day for each local reaction across all doses.

For participants in the VLA15 group with placebo administration in error, reactogenicity data after placebo administration will not be included in the derivation.

3.1.1.2. Systemic Events

Systemic events, including fever, fatigue, headache, muscle pain, and joint pain, are reported via the e-diary from Day 1 through Day 7 after vaccination, where Day 1 is the day of each dose of VLA15 or placebo. The derivations listed below for systemic events will be handled similarly to the way local reactions are handled for the presence for each participant, severity level, duration, and onset day:

- Presence (yes or no) of each systemic event on any day (Day 1 through Day 7) for each dose

- Presence (yes or no) of each systemic event on any day (Day 1 through Day 7) for any dose
- Presence (yes or no) of any systemic event on any day (Day 1 through Day 7) for each dose
- Presence (yes or no) of any systemic event on any day (Day 1 through Day 7) for any dose
- Maximum severity of each systemic event on any day (Day 1 through Day 7) for each dose
- Maximum severity of each systemic event on any day (Day 1 through Day 7) for any dose
- Maximum severity of any systemic event on any day (Day 1 through Day 7) for each dose
- Maximum severity of any systemic event on any day (Day 1 through Day 7) for any dose
- Duration of each systemic event after each dose and any dose
- Onset day of each systemic event after each dose and any dose

The grading scale for systemic events is provided in the protocol. However, the derivation of severity of each systemic event on each day should be based on the maximum severity reported in the e-diary or the AE CRF, if data are reported from both sources, or the e-diary alone if not reported in the AE CRF.

Fever is defined as a temperature of $\geq 100.4^{\circ}\text{F}$ ($\geq 38.0^{\circ}\text{C}$). The highest temperature for each day will be recorded in the e-diary. For reporting purposes, fever will be analyzed using the following temperature ranges:

- Mild ($\geq 38.0^{\circ}\text{C}$ to 38.4°C from the e-diary or mild grade from the AE CRF)
- Moderate ($> 38.4^{\circ}\text{C}$ to 38.9°C from the e-diary or moderate grade from the AE CRF)
- Severe ($> 38.9^{\circ}\text{C}$ to 40.0°C from the e-diary or severe grade from the AE CRF)
- Grade 4 ($> 40.0^{\circ}\text{C}$ from the e-diary or severe grade from the AE CRF plus documented $> 40.0^{\circ}\text{C}$ in the CRF query or other sources)

If any temperature is confirmed as incorrect, the correct temperature will be used for the analysis. Those for which the correct temperature is unknown will not be included in the analysis.

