8.3.3.4. Fever

In order to record information on fever, a digital thermometer will be given to the participant's parent(s)/legal guardian with instructions on how to measure the participant's oral temperature at home. Temperature will be collected in the evening daily for 7 days following vaccination (Days 1 through 7, where Day 1 is the day of vaccination) and at any time during the 7 days that fever is suspected. Fever is defined as an oral temperature of $\geq 100.4^{\circ}\text{F}$ ($\geq 38.0^{\circ}\text{C}$). The highest temperature for each day will be recorded in the e-diary. In the event of a fever on Day 7, temperature will be collected daily until the fever has resolved.

(1 day of temperature less than 100.4°F [38.0°C] in order to collect a stop date in the CRF). The parent(s)/legal guardian of a participant with a fever >104.0°F (>40.0°C) will be prompted to contact the investigator to assess the fever and perform an unscheduled visit as appropriate. Study staff must also contact the participant's parent(s)/legal guardian to obtain additional information if a temperature of ≥102.1°F (≥39.0°C) is entered into an e-diary. Temperature will be measured and recorded to 1 decimal place and then grouped into ranges for the analysis according to Table 4.

Table 4. Ranges for Fever

100.4°F to 101.1°F (≥38.0°C to 38.4°C)
101.2°F to 102.0°F (>38.4°C to 38.9°C)
102.1°F to 104.0°F (>38.9°C to 40.0°C)
>104.0°F (>40.0°C)

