
* EDP (with or without an associated AE or SAE): any pregnancy information is reported to Pfizer Safety using the Vaccine SAE Reporting Form and EDP Supplemental Form; if the EDP is associated with an SAE, then the SAE is reported to Pfizer Safety using the Vaccine SAE Reporting Form.
 
** EDB is reported to Pfizer Safety using the Vaccine SAE Reporting Form, which would also include details of any SAE that might be associated with the EDB.
 
*** Environmental or occupational exposure: AEs or SAEs associated with occupational exposure are reported to Pfizer Safety using the Vaccine SAE Reporting Form.
 
 When an AE or SAE occurs, it is the responsibility of the investigator to review all documentation (eg, hospital progress notes, laboratory reports, and diagnostic reports) related to the event. The investigator will then record all relevant AE or SAE information in the CRF. It is not acceptable for the investigator to send photocopies of the participant's medical records to Pfizer Safety in lieu of completion of the Vaccine SAE Reporting Form/AE or SAE CRF page. There may be instances when copies of medical records for certain cases are requested by Pfizer Safety. In this case, all participant identifiers, with the exception of the participant number, will be redacted on the copies of the medical records before submission to Pfizer Safety. The investigator will attempt to establish a diagnosis of the event based on signs, symptoms, and/or other clinical information. Whenever possible, the diagnosis (not the individual signs/symptoms) will be documented as the AE or SAE. 		
Assessment of Intensity		
The investigator will make an assessment of intensity for each AE and SAE reported during the study and assign it to 1 of the following categories:		
GRADE	If required on the AE page of the CRF, the investigator will use the adjectives MILD, MODERATE, and SEVERE to describe the maximum intensity of the AE. For purposes of consistency, these intensity grades are defined as follows:	
1	MILD	Does not interfere with participant's usual function.

2	MODERATE	Interferes to some extent with participant's usual function.
3	SEVERE	Interferes significantly with participant's usual function.

An event is defined as "serious" when it meets at least 1 of the predefined outcomes as described in the definition of an SAE, NOT when it is rated as severe.

Assessment of Causality

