3. ENDPOINTS AND BASELINE VARIABLES: DEFINITIONS AND CONVENTIONS

3.1. Primary Endpoints

3.1.1. Primary Safety Endpoints

Primary safety endpoints include both reactogenicity data and AEs collected from the e-diary and the AE CRF.

Based on feedback from the FDA on multiple vaccine programs, reactogenicity data will utilize both e-diary data (prompted local reactions and systemic events) and reactogenicity events reported in the AE CRF during the e-diary collection period.

Since the AE CRF does not designate a specific page to collect reactogenicity data for an untransmitted e-diary, Pfizer has adopted a process of providing a listing of AEs reported within 7 days after vaccination for the clinical team to review and determine (“flag”) which PTs should be considered reactogenicity events before the database lock. AEs reported on the same day of vaccination that are missing a start time are defaulted to AEs reported after vaccination. Following these review steps, those AEs reported within 7 days after vaccination that match flagged PTs will be considered reactogenicity data. If the same reactogenicity event is reported on the same day from both the e-diary and the AE CRF, the highest grade from the 2 data sources will be used for that specific day for analysis.

It should be noted that the data collection in the AE CRF is different from that of the e-diary:

- For redness, swelling, and fever, the measured size of redness and swelling at the injection site and temperature are recorded in the e-diary but not in the AE CRF. As the missing e-diary entries are monitored in an ongoing review of the prompted reactions reported in the AE CRF, any measurement recorded in the query response will be considered for the primary analysis, using the data handling memo for analysis purposes. For the 7 days, only the maximum grading from both sources will be used for the aggregated severity analysis.
- For pain at the injection site and all other systemic events, the severity grading algorithm for the e-diary data and the AE CRF may not be the same. Pfizer will choose the highest severity grade.

Any AEs recorded on the AE CRF for 7 days following study intervention administration (Day 1 through Day 7) that are considered local reactions or systemic events will be consolidated with the e-diary data and included in the reactogenicity report.

The subsections below describe how to derive each safety endpoint.

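### Outside the e-diary, SAP 3.1.1.2 counts a documented fever above 40.0°C as Grade 4 only if the AE CRF intensity is also severe, a condition absent from Protocol Table 4

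*SAP*

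**What the plan says.** Protocol 8.3.3.4 bands fever by measurement: "Temperature will be measured and recorded to 1 decimal place and then grouped into ranges for the analysis according to Table 4". The top range in Table 4 is >104.0°F (>40.0°C), and no AE intensity enters it.

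SAP 3.1.1.2 starts the same way, "For reporting purposes, fever will be analyzed using the following temperature ranges", but then attaches an AE CRF intensity to each range. The Moderate range, for example, takes readings of >38.4 to 38.9°C "from the e-diary or moderate grade from the AE CRF". Grade 4 takes an e-diary reading above 40.0°C, "or severe grade from the AE CRF plus documented" evidence of a temperature above 40.0°C from a CRF query or elsewhere. Daily severity is "based on the maximum severity reported in the e-diary or the AE CRF, if data are reported from both sources".

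SAP 3.1.1 recognises that the AE CRF does not hold the temperature itself. It states that "any measurement recorded in the query response will be considered for the primary analysis, using the data handling memo for analysis purposes", and that the highest grade from the two sources is carried into the 7-day summary.

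The AE CRF intensity scale in Protocol 10.3.4 is functional. Its moderate level is an event that "Interferes to some extent with" the child's usual function. SAP 2.1 says that no analysis differs from the protocol.

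**The concern.** A band defined by a thermometer reading has acquired a second condition that has nothing to do with temperature. A child with a documented 40.3°C who was only partly limited in activity is properly graded moderate on the AE CRF. That grading is not a site error, yet it keeps the fever out of the Grade 4 row.

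The non-diary route is meant to be used. SAP 5.3.1.1 relies on the AE CRF to fill missed e-diary days, and Protocol 8.11 has body temperature measured at unscheduled visits, so temperatures will exist outside the diary.

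The AE tables would not show the problem. SAP 3.1.1.3 and 6.1.2.1 remove non-serious reactogenicity events reported in the AE CRF during the diary period from the AE summaries. A non-serious fever placed too low would appear only in the lower fever row. The top fever row is likely to be a small count in this descriptive paediatric safety study, so one or two cases could change it visibly.

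**Working it through.** The plan gives no figure to reproduce here. The check is to apply the rules to cases.

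**Inputs.** Bands from SAP 3.1.1.2: 1 = 38.0 to 38.4°C, 2 = >38.4 to 38.9°C, 3 = >38.9 to 40.0°C, 4 = >40.0°C. AE CRF mild, moderate and severe map to 1, 2 and 3; severe becomes 4 if a temperature above 40.0°C is documented outside the diary. The higher of the e-diary and AE CRF grades is used.

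**Two codings.** Coding A follows SAP 3.1.1.2 literally. Coding B also bands the documented temperature by its value, which is one reading of SAP 3.1.1 and is what Table 4 implies. The temperature documented outside the diary is 40.3°C throughout.

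| E-diary value | AE CRF grade | A: literal 3.1.1.2 | B: temperature also banded |
|---|---|---|---|
| none | mild | 1 | 4 |
| none | moderate | 2 | 4 |
| none | severe | 4 | 4 |
| 38.2°C | moderate | 2 | 4 |
| 39.5°C | mild or moderate | 3 | 4 |
| 40.3°C | any | 4 | 4 |

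Three things follow.

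- For a documented temperature above 40.0°C, the codings differ only when the AE CRF grade is mild or moderate and no e-diary value is itself above 40.0°C.
- Every difference is in one direction: A is below B, by one to three grades. Measured against Table 4, the severity condition can remove a documented case from the top row and cannot add one.
- The child is still counted as having fever. The any-severity proportion is unchanged; only the distribution by maximum severity moves.

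**Size.** The documents give no rate of fever above 40.0°C, no share documented outside the diary and no share graded below severe. The following range is purely an assumption, to show scale:

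- VLA15 recipients: 2250 (Protocol 9.5) to 2662 (three quarters of the 3550 in SAP 2.3), each assumed to receive all 4 doses.
- Fever above 40.0°C after 0.05% to 0.2% of doses: 2250 × 4 × 0.0005 = 4.5, up to 2662 × 4 × 0.002 = 21.3 episodes.
- 10% to 20% documented only outside the diary, and 30% to 50% of those graded below severe: factors of 0.1 × 0.3 = 0.03 and 0.2 × 0.5 = 0.10.
- Product: 4.5 × 0.03 = 0.14, up to 21.3 × 0.10 = 2.1 episodes placed too low.

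These count dose-level episodes, not children, and the lower end is effectively none.

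**The case against.** The strongest defence is that the clause has a plainer purpose. AE CRF intensity stops at severe, so something must say when a severe entry becomes Grade 4, and the clause does that. The mild and moderate AE CRF entries can then be read as fallbacks for when no measurement exists, with SAP 3.1.1 governing when one does. SAP 3.1.1 sets no severity limit, and SAP 3.1.1.2 nowhere tells the analyst to ignore a measured temperature.

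For query responses this defence has force. A reader might infer that a documented fever above 40.0°C graded moderate is definitely tabulated at >38.4 to 38.9°C. The documents do not support that. SAP 3.1.1 may bring the queried value in, the data handling memo that would settle it is not part of the documents, and an e-diary value in a higher band would lift the grade anyway. But SAP 3.1.1 does not say how a queried temperature becomes a grade, so the two sections remain in conflict. For a temperature found only elsewhere, such as an unscheduled-visit or emergency-room reading, SAP 3.1.1 speaks only of query responses and does not help.

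It is also fair that the diary should catch most high fevers. Protocol 8.3.3.4 asks for a reading whenever fever is suspected and records the day's highest, and SAP 3.1.1.2 replaces values confirmed as wrong. That limits the number of cases, mainly to missed diary days and readings that never reached the diary. It does not repair the rule.

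**Conclusion.** The point holds as a minor defect of derivation. As worded, SAP 3.1.1.2 adds a functional-severity condition to a band that Protocol Table 4 defines by temperature alone. For queried temperatures, placement is unresolved between SAP 3.1.1 and 3.1.1.2. For temperatures documented only in other sources, the literal result is a lower band: the one matching the AE CRF grade, or the e-diary band if higher.

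The number affected is probably very small and cannot be computed from the documents; the 0.14 to 2.1 range rests wholly on assumed rates. A reader might also infer a bias in the comparison of VLA15 with placebo. The documents do not show one: the rule is the same in both arms, and those who evaluate safety are blinded. What is established is possible undercounting of the top fever row.

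**What to change.** In SAP 3.1.1.2, define Grade 4 fever for analysis as any temperature above 40.0°C on Days 1 to 7 documented in the e-diary, a CRF query or another source, regardless of AE CRF intensity. This brings the section into line with Protocol Table 4 and with the intent of SAP 3.1.1. It should stand in the SAP and not be left to the data handling memo.

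The cost is one clause, using temperatures that are already documented. The Grade 4 fever count may come out slightly higher. The change concerns tabulation only and touches no clinical procedure.

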3.1.1.3. Adverse Events and Serious Adverse Events

Standard algorithms for handling missing AE dates and missing AE severity will be applied as described in the Pfizer vaccine data standard rules. Completely missing AE start dates will not be imputed.

The following derivations (yes/no) will be included for each participant:

- Any AE reported within 30 days (Day 1 through Day 31) after each dose and after any dose
- Any related AE reported within 30 days (Day 1 through Day 31) after each dose and after any dose
- Any immediate AE (AE start time is within 30 minutes after vaccination) reported after each dose and after any dose
- Any severe AE reported within 30 days (Day 1 through Day 31) after any dose
- Any AE leading to study withdrawal after the first dose
- Any AE leading to death after the first dose

AE reports will exclude any reactogenicity events (but not exclude reactogenicity SAEs) reported in the AE CRF during the e-diary collection period.

- Any AESI reported during the study after the first dose

Because this study does not include active surveillance for LD, diagnosis terms under the ICD-10 code for LD (A69.2) that represent clinical diagnoses of acute LD (early, early disseminated, or late manifestations) made by a qualified healthcare provider will be considered AESIs for this study. The AESI PTs will be included in the data handling memo before the database lock.

- NDCMCs reported during the study after the first dose
- SAEs reported during the study after the first dose (including reactogenicity events reported in the AE CRF during the e-diary collection period)
- Related SAEs reported during the study after the first dose (including reactogenicity events reported in the AE CRF during the e-diary collection period)

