7. DISCONTINUATION OF STUDY INTERVENTION AND PARTICIPANT DISCONTINUATION/WITHDRAWAL

7.1. Discontinuation of Study Intervention

It may be necessary for a participant to permanently discontinue study intervention. Reasons for permanent discontinuation of study intervention include the following: AEs; parent(s)/legal guardian or participant request; investigator request; pregnancy; and protocol deviation (including no longer meeting all inclusion criteria or meeting 1 or more exclusion criteria).

Note that discontinuation of study intervention does not represent withdrawal from the study. If study intervention is permanently discontinued, the participant should remain in the study to be evaluated for safety. All participants for whom study intervention was discontinued after the last dose of the primary series or the booster dose will be followed for safety and immunogenicity, as applicable. See the [SoA](#) for data to be collected at the time of discontinuation of study intervention and follow-up for any further evaluations that need to be completed.

In the event of discontinuation of study intervention, it must be documented on the appropriate CRF/in the medical records whether the participant is discontinuing further receipt of study intervention or also from study procedures, postvaccination study follow-up, and/or future collection of additional information.

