7.2.1. Withdrawal of Consent

Participants who request (or whose parent(s)/legal guardian request) to discontinue receipt of study intervention will remain in the study and must continue to be followed for protocol-specified follow-up procedures. The only exception to this is when a participant or participant's parent(s)/legal guardian specifically withdraws consent for any further contact with them or persons previously authorized by the participant to provide this information. Participants or participants' parent(s)/legal guardian should notify the investigator in writing of the decision to withdraw consent from future follow-up, whenever possible. The withdrawal of consent should be explained in detail in the medical records by the investigator, as to whether the withdrawal is only from further receipt of study intervention or also from study procedures and/or postvaccination study follow-up, and entered on the appropriate CRF page. In the event that vital status (whether the participant is alive or dead) is being measured, publicly available information should be used to determine vital status only as appropriately directed in accordance with local law.

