8.4.1. Time Period and Frequency for Collecting AE and SAE Information

The time period for actively eliciting and collecting AEs and SAEs ("active collection period") for each participant begins from the time the participant/parent(s)/legal guardian provides informed consent, which is obtained before the participant's participation in the study (ie, before undergoing any study-related procedure and/or receiving study intervention), through and including a minimum of 1 month after each vaccination. NDCMCs and SAEs will be collected throughout the study.

Follow-up by the investigator continues throughout the active collection period and until the AE or SAE or its sequelae resolve or stabilize at a level acceptable to the investigator.

When a clinically important AE remains ongoing at the end of the active collection period, follow-up by the investigator continues until the AE or SAE or its sequelae resolve or stabilize at a level acceptable to the investigator and Pfizer concurs with that assessment.

For participants who are screen failures, the active collection period ends when screen failure status is determined.

If the participant or his or her parent(s)/legal guardian withdraws from the study and also withdraws consent for the collection of future information, the active collection period ends when consent is withdrawn.

If a participant permanently discontinues or temporarily discontinues study intervention because of an AE or SAE, the AE or SAE must be recorded on the CRF and the SAE reported using the Vaccine SAE Reporting Form.

Investigators are not obligated to actively seek information on AEs or SAEs after the participant has concluded study participation. However, if the investigator learns of any SAE, including a death, at any time after a participant has completed the study, and they consider the event to be reasonably related to the study intervention, the investigator must promptly report the SAE to Pfizer using the Vaccine SAE Reporting Form.

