6.4.2. Study Conduct and Participant Disposition

The number and proportion of participants enrolled, randomized, and vaccinated at each dose will be included in the participant disposition summary. In addition, participants who received each dose, completed the study, and who were withdrawn after each dose and any dose, along with the reasons for withdrawal, will be tabulated by vaccine group and for all participants included in the randomized population. The reasons for withdrawal will be those specified in the database.

The e-diary completion rate will be summarized for the safety population by vaccine group, as well as summarized for the categorized days specified in [Section 3.4.1](#).

Standard listings will be generated, including, but not limited to, participants who withdraw during the study, participants who are excluded from the analysis populations, participants with major protocol violations, and participants who do not receive the vaccine as randomized.

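### No SAP table identifies the AEs that led to stopping study vaccination, or the reasons for stopping, because the SAP tracks only withdrawal from the study

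*SAP*

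**What the plan says.** The protocol separates two states. Section 7.1 says: "Note that discontinuation of study intervention does not represent withdrawal from the study". AEs come first in its list of reasons for stopping ("Reasons for permanent discontinuation of study intervention include the following: AEs"), and it gives the consequence: "If study intervention is permanently discontinued, the participant should remain in the study to be evaluated for safety". Section 7.2.1 applies the same rule to families who ask to stop doses. They "will remain in the study and must continue to be followed for protocol-specified follow-up procedures", unless consent to further contact is withdrawn.

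The protocol expects some children to be stopped. The risk table in 2.3.1 lists exclusion from further vaccination after significant reactions or AEs as a mitigation. Recording is also covered, in 8.4.1, with the CRF as the place of record: "If a participant permanently discontinues or temporarily discontinues study intervention because of an AE or SAE, the AE or SAE must be recorded".

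The SAP follows only one of the two states. The only discontinuation category in 3.1.1.3, apart from death, is "Any AE leading to study withdrawal after the first dose". The disposition summary in 6.4.2 gives the numbers who received each dose, and those "who were withdrawn after each dose and any dose, along with the reasons for withdrawal, will be tabulated by vaccine group". It asks for no reasons for stopping vaccination alone. The only intercurrent event named in SAP 2.2.1.1 is not completing the study.

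**The concern.** This is a four-dose trial whose only objective is safety. How many children in each arm stopped vaccination because of an AE is a natural tolerability question, and the protocol requires the responsible AE to be recorded. With both documents followed exactly, the report cannot answer it. A child stopped after Dose 1 and followed to Month 24 is not a study withdrawal, so neither the AE derivation nor the withdrawal reasons pick the child up. The more closely sites follow protocol 7.1, the fewer AE-related stops the study-withdrawal category captures.

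A second consequence concerns the dose-specific safety populations in SAP section 4. They shrink at Doses 2 to 4 as children stop. Without AE-related stops by arm, a reader cannot judge how far the later-dose rates come from children selected for having tolerated earlier doses.

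**Working it through.** The plan states no figure for this point, so there is none to reproduce. The check is a reading of the SAP's derivations and tables, followed by a range for the number affected.

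**Step 1. Where an AE that ends vaccination would be counted, for a child who stays in the study**

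| Type of event | Specified output | Shown as having ended vaccination? |
|---|---|---|
| Nonserious, starts Day 1-31, not flagged as reactogenicity | Any AE within 30 days (SAP 3.1.1.3), by MedDRA term (6.5.1) | No |
| Nonserious local or systemic reaction, Day 1-7 | Reactogenicity report (3.1.1); removed from AE reports (3.1.1.3) | No |
| SAE, NDCMC or AESI, any time after Dose 1 | Its own category in 3.1.1.3 | No |
| Nonserious, starts outside Day 1-31, neither NDCMC nor AESI | None specified | No |

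The last column is the same in every row: the link to stopping is missing throughout. The event itself is missing only in the last row.

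**Step 2. How much time the last row covers**

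Only AEs before the booster can cost a child a later dose. The inputs are the Day 1-31 windows in SAP 3.1.1.3 and the booster window of 535 to 555 days after Visit 1 in the protocol's schedule of activities.

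- Days covered by the three windows: 3 × 31 = 93.
- Days not covered: 535 − 93 = 442, up to 555 − 93 = 462.
- Share not covered: 442/535 = 82.6%, up to 462/555 = 83.2%, so about 83%.

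This is a share of time, not of events. Under protocol 8.4.1, nonserious AEs are actively collected for a minimum of one month after each dose, so few may be recorded later. An AE that stops vaccination must be recorded.

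**Step 3. How many children**

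The protocol (9.5) plans about 2250 VLA15 recipients. Two inputs are assumptions, because neither document gives them: the share stopping for an AE (0.2% to 1%) and the share of those who also leave the study (0% to 50%).

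Not counted = N × share stopping × (1 − share leaving)

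- Low end: 2250 × 0.002 × 0.5 = 2.25.
- High end: 2250 × 0.01 × 1 = 22.5.

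The SAP (2.3) plans about 3550 randomised 3:1, which gives 3550 × 0.75 = 2662.5 on VLA15. The range is then 2662.5 × 0.002 × 0.5 = 2.7 to 2662.5 × 0.01 = 26.6.

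**The case against.** The strongest reply is that little is lost. Most of these events are tabulated somewhere, as Step 1 shows. The numbers receiving each dose are tabulated by arm, so falling dose counts are visible. AEs are also a listed reason for leaving the study (protocol 7.2), so the existing derivation is legitimate. AE-related discontinuation is not one of the stated primary endpoints, so no endpoint goes unanalysed. The listings in SAP 6.4.2 are not presented as exhaustive, so a listing of children who stopped could still be produced.

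All of this stands, and it limits the point to a reporting gap. It does not close the gap. Dose counts show that children stopped but not why, general AE tables do not say which events ended vaccination, and an output that is allowed but not specified is not a plan.

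Two stronger readings are tempting, and the documents support neither.

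- A reader might infer that AEs ending vaccination appear in no table at all. That is true only of the last row in Step 1.
- A reader might infer that the plan would hide a clear difference between arms. With 34 of 2250 v 4 of 750 stopping for an AE, the difference is 0.98 points (95% Miettinen-Nurminen interval 0.07 to 1.68). If about 80% stay in the study, 7 v 1 remain visible, a difference of 0.18 (−0.45 to 0.54). That contrast depends on the assumed rates. With 22 v 4, full counting gives 0.44 (−0.44 to 1.06), which already includes zero. Nor does the SAP commit to a difference interval for this category: 6.1.2.1 specifies within-arm Clopper-Pearson intervals, and 6.5.1 commits to difference intervals only for Tier 1 and Tier 2 events.

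**Conclusion.** The point holds as a gap in reporting. No specified SAP table identifies AEs that led to discontinuation of study intervention, or the reasons for it, although the protocol defines that state separately and keeps the children in follow-up. This follows from the text and depends on no assumed rate.

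The size is unknown. On the assumptions in Step 3, about 2 to 22 VLA15 recipients would not be counted as AE-related discontinuations, or about 3 to 27 at the SAP's sample size. No difference between arms is claimed, and the primary endpoints are not affected. It is a cheap improvement.

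**What to change.** In SAP 3.1.1.3, add a derivation: *any AE leading to permanent discontinuation of study intervention, after each dose and after any dose*. It should:

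- count the child whether or not the child leaves the study;
- have no Day 1-31 limit;
- be exempt from the rule in the same section that removes nonserious reactogenicity events from AE reports, since otherwise children stopped for a reaction would drop out again;
- be summarised by vaccine group and age group with the intervals in SAP 5.2.1.

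In SAP 6.4.2, tabulate reasons for discontinuing study intervention, using the list in protocol 7.1, separately from reasons for study withdrawal.

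The cost is SAP wording and two tables. One check is needed first. Protocol 7.1 allows the discontinuation to be documented on the CRF or in the medical records, and 8.4.1 requires the AE on the CRF without naming a field that ties it to stopping. The sponsor should confirm that the CRF holds that link. No clinical rule changes.
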